7.3 Subject Population(s) for Analysis

Subjects will be elders age 50 and older with normal cognition, mild cognitive impairment, or mild AD.

8 Safety and Adverse Events

8.1 Definitions

Adverse Event

An *adverse event* (AE) is any symptom, sign, illness or experience that develops or worsens in severity during the course of the study. Intercurrent illnesses or injuries should be regarded as adverse events. Abnormal results of diagnostic procedures are considered to be adverse events if the abnormality:

- results in study withdrawal
- is associated with a serious adverse event
- is associated with clinical signs or symptoms
- leads to additional treatment or to further diagnostic tests
- is considered by the investigator to be of clinical significance

Serious Adverse Event

Adverse events are classified as serious or non-serious. A *serious adverse event* is any AE that is:

- fatal
- life-threatening
- requires or prolongs hospital stay
- results in persistent or significant disability or incapacity
- a congenital anomaly or birth defect
- an important medical event

Important medical events are those that may not be immediately life threatening, but are clearly of major clinical significance. They may jeopardize the subject, and may require intervention to prevent one of the other serious outcomes noted above. For example, drug overdose or abuse, a seizure that did not result in in-patient hospitalization, or intensive treatment of bronchospasm in an emergency department would typically be considered serious.

All adverse events that do not meet any of the criteria for serious should be regarded as *non-serious adverse events*.

Adverse Event Reporting Period

The study period during which adverse events must be reported is normally defined as the period from the initiation of any study procedures to the end of the study treatment follow-up. For this study, the study drug follow-up is defined as 24 hours following administration of study drug. Subjects will receive a telephone call 24 hours after the PET scan for adverse event reporting.

Preexisting Condition

A preexisting condition is one that is present at the start of the study. A preexisting condition will be recorded as an adverse event if the frequency, intensity, or the character of the condition worsens during the study period.

General Physical Examination Findings

At screening, any clinically significant abnormality will be recorded as a preexisting condition. At the end of the study, any new clinically significant findings/abnormalities that meet the definition of an adverse event will also be recorded and documented as an adverse event.

Post-study Adverse Event

All unresolved adverse events will be followed by the investigator until the events are resolved, the subject is lost to follow-up, or the adverse event is otherwise explained. At the last scheduled visit, the investigator will instruct each subject to report any subsequent event(s) that the subject, or the subject's personal physician, believes might reasonably be related to participation in this study. The investigator will notify IRB and FDA of any death or adverse event occurring at any time after a subject has discontinued or terminated study participation that may reasonably be related to this study.

Abnormal Laboratory Values

A clinical laboratory abnormality will be documented as an adverse event if any one of the following conditions is met:

- The laboratory abnormality is not otherwise refuted by a repeat test to confirm the abnormality
- The abnormality suggests a disease and/or organ toxicity
- The abnormality is of a degree that requires active management; e.g. change of dose, discontinuation of the drug, more frequent follow-up assessments, further diagnostic investigation, etc.

Hospitalization, Prolonged Hospitalization or Surgery

Any adverse event that results in hospitalization or prolonged hospitalization will be documented and reported as a serious adverse event unless specifically instructed otherwise in this protocol. Any condition responsible for surgery should be documented as an adverse event if the condition meets the criteria for an adverse event.

Neither the condition, hospitalization, prolonged hospitalization, nor surgery are reported as an adverse event in the following circumstances:

- Hospitalization or prolonged hospitalization for diagnostic or elective surgical procedures for a preexisting condition. Surgery should **not** be reported as an outcome of an adverse event if the purpose of the surgery was elective or diagnostic and the outcome was uneventful.
- Hospitalization or prolonged hospitalization required to allow efficacy measurement for the study.
- Hospitalization or prolonged hospitalization for therapy of the target disease of the study, unless it is a worsening or increase in frequency of hospital admissions as judged by the clinical investigator.

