5.9.4 Return or Destruction of Study Drug

Any unused radiopharmaceutical will be on site and documented in the study files.

6 Study Procedures

This study will involve up to 5 outpatient visits. See schedule below.

At the first screening visit, subjects will sign informed consent, undergo history and physical and neurological examination, neuropsychological testing, and have blood drawn routine safety laboratories. Additional screening visits may be required to complete all procedures. Additional visits will be required for brain MRI. Flexibility is allowed in screening procedures such that procedures may be performed in any order and may be performed on the same day if schedule allows for subject convenience. Subjects who already had screening procedures performed under a previous research protocol do not need to have them repeated unless performed more than 12

months prior to the ¹⁸F-THK-5351 PET scan. A total of 3 screening visits are anticipated. However, additional visits may be necessary if certain tests must be scheduled on different days due to scheduling.

Up to two study visits will be required. One visit will be for the ¹⁸F-THK-5351 PET scan and the second for the optional lumbar puncture. Subjects may decline the lumbar puncture and still participate in other parts of the study. If schedule allows, the ¹⁸F-THK-5351 PET and LP could be performed on the same day.

¹⁸F-THK-5351 PET scans and LP must be completed within 12 months of the brain MRI.

Study Schedule

Study Procedures	Screen ^a	Study ^b	
	≤12 months	Visit 1	Visit 2
Informed consent	X		
Medical/psychiatric history	X		
Inclusion/exclusion criteria	X	X	X
Neuropsychological testing	X		
MRI	X		
¹⁸ F-THK-5351 PET ^c		X	
Lumbar puncture ^{c, d}			X
Laboratory determinations ^e	X	X	
Neurological examination	X		
Vital signs	X		
Height and weight	X	X	
Adverse events ^f	X	X	X

a. Screening procedures may be performed in any order and may be performed on the same day if schedule allows for subject convenience. Subjects who already had screening procedures performed under a different protocol do not need to have them repeated unless performed more than 12 months prior to inclusion in this study. Up to 3 screening visits are anticipated. However, additional visits may be necessary if certain tests must be scheduled on different days due to scheduling.

b. Study procedures must be completed within 12 months of MRI.

c. ¹⁸F-THK-5351 PET and LP may be performed on same day.

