d. Lumbar puncture is optional.

e. Laboratory determinations here include complete blood count, basic metabolic panel, liver functions tests, thyroid stimulating hormone, and urinalysis.

f. Adverse event reporting to be performed at Visit 1 after the PET scan is completed. Subject will be called by telephone 24 hours after the PET scan for follow up adverse event reporting.

7 Statistical Plan

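### The adverse-event reporting period ends 24 hours after the radioligand, so it has closed before any lumbar puncture held more than 24 hours after PET, and no scheduled contact follows that puncture

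*Combined protocol and SAP*

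**What the plan says.** Section 8.1 (Adverse Event Reporting Period) says that the reporting period is normally "the period from the initiation of any study procedures to the end of the study treatment follow-up". It then sets the end point: "For this study, the study drug follow-up is defined as 24 hours following administration of study drug". The LP does not enter this definition.

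Section 6 provides for up to two study visits, one for the "PET scan and the second for the optional lumbar puncture". Combining them is allowed but not required: if the schedule permits, "PET and LP could be performed on the same day". The only outer limit is that "PET scans and LP must be completed within 12 months of the brain MRI". No maximum interval between PET and LP is given, in either order.

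The adverse-event row of the Study Schedule is marked at screening, Visit 1 and Visit 2. Its footnote f gives details for PET only: "Adverse event reporting to be performed at Visit 1 after the PET scan is completed", and "Subject will be called by telephone 24 hours after the PET scan for follow up adverse event reporting". Section 8.1 repeats the call after PET. Neither place has a call after the LP or says when at Visit 2 the questioning takes place.

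**The concern.** The LP is the more invasive of the two study-visit procedures, yet the period and the call are both anchored to the tracer, which Section 5.1 does not expect to have a pharmacological effect. If the LP is on a later day, the schedule asks for adverse events at a visit that Section 8.1 places after the reporting period. Section 8.2 requires recording of all adverse events within the study period, so staff cannot tell from the text whether a non-serious event that starts on the evening after such an LP has to be recorded.

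What is at stake is how completely harms of a study procedure are captured. Half of the target sample (30 of 60) is cognitively impaired, and under Section 3.1.1 some will take part through a representative's consent. Waiting for these subjects to remember and volunteer an event is a weak method. Sections 8.5 and 8.6 provide no stopping rule and no data and safety monitoring board, so oversight depends on individual event reports.

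**Working it through.** No power, sample-size or alpha figure is involved. The check is a timeline.

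**Inputs.** Injection is at time 0. The period closes at 24 h (Section 8.1). One call is made 24 h after PET (Section 8.1; Section 6, footnote f). The call is timed from the scan and the period from the injection; that small difference is ignored here. The LP is at L hours after injection. There is one LP per subject (Section 3.1.5) and there are up to 60 subjects (Section 3.1.1). The values of L are illustrations, because the plan gives no LP timing.

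**Formula.** For an LP after injection, post-LP time inside the reporting period = max(0, 24 − L).

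| L | Post-LP time inside the period | Scheduled contacts after the LP |
|---|---|---|
| 4 h (same day) | 24 − 4 = 20 h | 1 (the call) |
| 48 h | 0 h | 0 |
| 168 h (7 days) | 0 h | 0 |
| 720 h (30 days) | 0 h | 0 |

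**LP on an earlier day than PET.** The period is still open, and two contacts follow: the PET visit and the call. Neither is tied to the LP. With only the 12-month limit from MRI, they may come weeks after it, so a contact exists but need not be prompt.

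**LP on the next day but within 24 h of injection.** At L = 19, for example, 24 − 19 = 5 h of the period remain, and the call falls about 5 h after the LP.

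**What the other provisions reach**, for an LP more than 24 h after PET:

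- Section 8.2 has the investigator question the subject at each contact. This covers events present at the LP visit but creates no later contact.
- Section 8.1 (Post-study Adverse Event) has subjects told, at the last scheduled visit, to report later events that they or their physician believe related. For these subjects that visit is the LP visit, and the instruction is not limited to serious events. It depends on the subject acting.
- The same part of Section 8.1 requires both the IRB and the FDA to be told of a related death, and likewise of an "adverse event occurring at any time after a subject has discontinued or terminated study participation that may reasonably be related to this study". The investigator must first learn of the event.
- Section 8.2 covers serious, possibly related events after the period.
- Section 8.3.1 covers Unanticipated Problems, serious or not. Section 8.2 requires these to be unexpected and to suggest greater risk than was known, so a non-serious event already described for the procedure would generally not qualify.

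None of these is an active contact after the LP. The remainder is non-serious events that start after the subject leaves.

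**After the fix.** Every LP done under this protocol would have at least 24 h inside the period. Extra calls are at most 60 subjects × 1 LP = 60.

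**The case against.** The strongest reply is that Section 8.1 is loosely worded and should be read with the rest of the plan. The period is only what is normally used, an adverse event is anything arising during the course of the study, Visit 2 carries an adverse-event mark, and unresolved events are followed until they resolve. Subjects with a later LP are told on the LP day itself to report what follows. On this view there is a wording mismatch and one missing telephone call, after an optional procedure, in a study with no safety endpoint (Section 3.4). Much of this stands, and it limits the point to delayed non-serious events. It does not remove the point: the sentence specific to this study still fixes 24 hours from the radioligand, and no text schedules a contact after a later LP.

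Three stronger readings are tempting, and the documents do not support them.

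- A reader might infer that adverse events of the LP are not collected at all. The Visit 2 mark, the questioning at each contact and the instruction to report say otherwise.
- A reader might treat the length of time since the period closed as the size of the gap. With PET on the MRI day and the LP at the limit, that could be close to 12 months. It measures how long ago the tracer window ended, not uncovered LP risk: the post-LP time inside the period is 0 h at 48 hours and at 12 months alike.
- A reader might assume that many subjects are affected or that a group comparison is distorted. LP uptake and timing are not given. Section 3.1.6 lets results from procedures done within a year of PET be reused, so some LPs may not take place under this protocol. No safety comparison is planned.

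**Conclusion.** The point holds in a limited form and should be corrected. Under the text as written, an LP done under this protocol more than 24 hours after PET falls after the reporting period, with 0 hours of cover in that period and 0 scheduled contacts afterwards, while the schedule still expects adverse events at that visit. The practical loss is active capture of non-serious events that begin after the subject leaves.

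This rests on the plain reading of the Section 8.1 end point and on Section 6 permitting, not requiring, same-day procedures. How many subjects it affects cannot be derived. The consent form was not in the text reviewed and may carry advice for after an LP; no claim is made about it. The primary SUVR analysis is unaffected.

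**What to change.** **Section 8.1.** End the reporting period 24 hours after the last study procedure performed under this protocol, PET or LP, or after a longer interval if the investigator fixes one. The documents give no follow-up interval for the LP; 24 hours simply matches the tracer.

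**Section 6, footnote f.** Add adverse-event questioning after the LP at Visit 2, and one telephone call about 24 hours after any LP not done on the PET day, whether before or after PET. Call the surrogate as well where one gave consent. For a same-day LP the existing call after PET serves.

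Keep the rules in Sections 8.1 to 8.3 for unresolved, serious, related and unanticipated later events.

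**Cost.** Two sentences and at most 60 calls. The number falls with every LP that is declined, done on the PET day, or reused from another protocol. No change to the imaging or its analysis is needed.

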8.2 Recording of Adverse Events

At each contact with the subject, the investigator will seek information on adverse events (AEs) by specific questioning and, as appropriate, by examination. Information on all adverse events will be recorded immediately in the source document. All clearly related signs, symptoms, and abnormal diagnostic procedures results will be recorded in the source document.

All adverse events occurring during the study period will be recorded. The clinical course of each event will be followed until resolution, stabilization, or until it has been determined that the study treatment or participation is not the cause. Serious adverse events that are still ongoing at the end of the study period will be followed up to determine the final outcome. Any serious adverse event that occurs after the study period and is considered to be possibly related to the study treatment or study participation will be recorded and reported immediately.

As per CUMC IRB's Policy, Unanticipated Problems will be defined as follows:

Unanticipated Problem (UP) is any incident, experience or outcome involving risk to subjects or others in any human subjects research that meets all of the following criteria:

- Unexpected (in terms of nature, severity or frequency) given (a) the research procedures that are described in the IRB-approval protocol and informed consent document and (b) the characteristics of the subject population being studied;
- Related or possibly related to participation in such research (i.e., there is a reasonable possibility that the incident, experience or outcome may have been caused by the procedures involved in such research); and
- Suggests that the research places subjects or others at a greater risk of harm (including physical, psychological, economic or social harm) than was previously known or recognized (HHS IRB Guidance, Section I).

The following AEs will be considered Unexpected Problems:

- A single occurrence of a serious, unexpected event that is uncommon and strongly associated with drug exposure
- A single occurrence, or a small number of occurrences, of a serious, unexpected event that is not commonly associated with drug exposure
- Multiple occurrences of an AE that, based on an aggregate analysis, are determined not to be isolated occurrences and involve risk to human subjects
- An AE that is described or addressed in the investigator's brochure, protocol or informed consent documents (a Described AE), but occurs at a specificity or severity that is inconsistent with prior observations
- A serious Described AE, but for which the rate of occurrence represents a clinically significant increase in the expected rate of occurrence
- Any other AE or safety finding that would cause the sponsor to modify the investigator's brochure, study protocol or informed consent documents or would prompt other action by the IRB to ensure the protection of human subjects (2009 FDA Guidance, Section III (A)).

8.3 Reporting of Serious Adverse Events

8.3.1 IRB Notification by Investigator

At the time of the Occurrence of an Unanticipated Problem:

Each UP will be reported to the IRB, whether or not (a) it is serious or non-serious or (b) it occurs at a site at which the PI is conducting the research.

The UP will be reported promptly, but not later than one week following the occurrence of the UP or the PI's acquiring knowledge of the UP.

The PI will make the determination as to whether an incident, experience or outcome constitutes a UP.

Each Unanticipated Problem will be reported to the IRB using the Unanticipated Problem Report module in Rascal.

The investigator must conclude in the Unanticipated Problem Report whether the protocol and/or consent form(s) should be modified as the result of the UP. If the protocol and/or consent document(s) requires a revision, a modification must be submitted in Rascal.

At the Time of Continuing Review of a Protocol:

At the time of continuing review of a protocol, the PI will submit a summary of all UPs that occurred during the review period and since the beginning of the study. The summary for each UP should include:

- The number of subjects who experienced the UP;

- The investigator's determination as to whether or not the UP was serious;
- The investigator's determination as to the UP's relationship to the study procedures (e.g., definitely related, probably related or possibly related).

8.3.2 FDA Notification by Investigator

The principal investigator shall notify the FDA by telephone or by facsimile transmission of any unexpected fatal or life-threatening experience associated with the use of the drug as soon as possible but no later than 7 calendar days from the investigator's original receipt of the information.

If a previous adverse event that was not initially deemed reportable is later found to fit the criteria for reporting, the principal investigator will submit the adverse event in a written report to the FDA as soon as possible, but no later than 15 calendar days from the time the determination is made.

8.4 Unblinding Procedures

N/A

8.5 Stopping Rules

N/A

8.6 Medical Monitoring

We will not have a specific Data and Safety Monitoring Board. Adverse events will be documented in the patient's chart. Notification of UPs to the IRB and SUSARs to the FDA will take place as described in Section 8.3.

9 Data Handling and Record Keeping

9.1 Confidentiality

Information about study subjects will be kept confidential and managed according to the requirements of the Health Insurance Portability and Accountability Act (HIPAA). Those regulations require a signed subject authorization informing the subject of the following:

- What protected health information (PHI) will be collected from subjects in this study
- Who will have access to that information and why
- Who will use or disclose that information
- The rights of a research subject to revoke their authorization for use of their PHI.

In the event that a subject revokes authorization to collect or use PHI, the investigator, by regulation, retains the ability to use all information collected prior to the revocation of subject authorization. For subjects that have revoked authorization to collect or use PHI, attempts should be made to obtain permission to collect at least vital status (i.e. that the subject is alive) at the end of their scheduled study period.

9.2 Source Documents

Source documents will be used to record data for this study. Source documents will be kept in secure location. For the PET visit, a checklist will be used to ensure all study procedures are completed.

9.3 Case Report Forms

Case report forms (CRFs) will be used as the primary research data collecting tool. CRFs may also be source documents in some instances. CRFs will be kept in a secure location.

10 Study Monitoring, Auditing, and Inspecting

10.1 Study Monitoring Plan

This study will be monitored by the Principal Investigator. [name] will submit annual progress reports to the FDA within 60 days of the anniversary of the date that the IND became active (the date clinical studies were permitted to begin) in accordance with 21 CFR 312.33.

11 Ethical Considerations

This study is to be conducted according to US and international standards of Good Clinical Practice (FDA Title 21 part 312 and International Conference on Harmonization guidelines), applicable government regulations and Institutional research policies and procedures.

This protocol and any amendments will be submitted to a properly constituted independent Institutional Review Board (IRB), in agreement with local legal prescriptions, for formal approval of the study conduct. The decision of the IRB concerning the conduct of the study will be made in writing to the investigator and a copy of this decision will be provided to the sponsor before commencement of this study. The investigator should provide a list of EC/IRB members and their affiliate to the sponsor.

All subjects for this study will be provided a consent form describing this study and providing sufficient information for subjects to make an informed decision about their participation in this study. See attached copy of the Subject Informed Consent Form. This consent form will be submitted with the protocol for review and approval by the IRB for the study. The formal consent of a subject, using the IRB-approved consent form, must be obtained before that subject is submitted to any study procedure. This consent form must be signed by the subject or legally acceptable surrogate, and the investigator-designated research professional obtaining the consent.

12 Study Finances

